4.2 Inclusion Criteria

Each patient must meet the following criteria to be enrolled in this study.

1. be male with a diagnosis of congenital hemophilia A or B of any severity
2. have one of the following:
 - a. a positive inhibitor test $BU \geq 5$ (as confirmed at screening by the institutional lab, with the exception being for patients <12 kg where samples will only be collected centrally), OR
 - b. an inhibitor test $BU < 5$ (as confirmed at screening by the institutional lab, with the exception being for patients <12 kg where samples will only be collected centrally) but expected to have an anamnestic response to FVIII or FIX, as demonstrated by a history of a high-responding inhibitor manifested by a previous anamnestic response, defined as a peak inhibitor titer > 5 BU after re-exposure to factor concentrates, precluding the use of FVIII or FIX products to treat or prevent bleeding, OR
 - c. an inhibitor test $BU < 5$ (as confirmed at screening by the institutional lab, with the exception being for patients <12 kg where samples will only be collected centrally) but expected to be refractory to FVIII or FIX, as demonstrated by the patient's history of previous failure to respond to FVIII or FIX concentrates, even in the absence of a documented anamnestic response, precluding the use of FVIII or FIX products to treat or prevent bleeding episodes.
3. be ≥ 6 months to ≤ 75 years of age; different age restrictions may apply per local regulation and ethical considerations (enrollment of children <12 years of age will not begin until after review of data from the [PERSEPT 2](#) study by the DMC)
4. be scheduled for an elective surgical or other invasive procedure
5. be capable of understanding and willing to comply with the conditions of the protocol OR in the case of a patient <18 years of age, parent(s)/legal guardian(s) must be capable of understanding and willing to comply with the conditions of the protocol
6. have read, understood, and provided written Informed Consent (patient and/or parent(s)/legal guardian(s) if the patient is <18 years of age) or Assent, if applicable

4.3 Exclusion Criteria

Patients who meet any of the following criteria will be excluded from the study.

1. have any coagulation disorder other than hemophilia A or B
2. be immunosuppressed (ie, the patient should not be receiving systemic immunosuppressive medication; CD4 counts at screening should be $>200/\mu\text{l}$)
3. known intolerance to LR769 or any of its excipients
4. currently receiving ITI therapy
5. have a known allergy or hypersensitivity to rabbits
6. have platelet count $<100,000/\mu\text{L}$
7. have received an investigational drug within 30 days of the planned first LR769 administration, or is expected to receive such drug during participation in this study (with the exception of patients who are or were participating in another LR769 study, eg, a study assessing the treatment of bleeding episodes with LR769)
8. have a clinically relevant hepatic (aspartate aminotransferase [AST] and/or alanine aminotransferase [ALT] >3 times the ULN and/or renal impairment (creatinine >2 times the ULN)
9. have a history of arterial and/or venous thromboembolic events (such as myocardial infarction, ischemic strokes, transient ischemic attacks, DVT, or PE) within 2 years prior to the planned first dose of LR769, uncontrolled arrhythmia, or current New York Heart Association (NYHA) functional classification score of stages II – IV
10. have an active malignancy (those with non-melanoma skin cancer are allowed)
11. have any life-threatening disease or other disease or condition which, according to the investigator's judgment, could imply a potential hazard to the patient, or interfere with the trial participation or trial outcome (eg, a history of non-responsiveness to bypassing products)
12. be using aspirin, NSAIDS, herbs, natural medications, or other drugs with platelet inhibitory properties within one week prior to surgery and for the duration of treatment with LR769
13. have active gastric or duodenal ulcer disease

5 STUDY TREATMENT(S)

5.1 Description of Treatment(s)

5.1.1 Study Drug

Coagulation Factor VIIa (Recombinant), LR769, is a pure FVIIa product produced using recombinant technology. It will be provided in a vial as a lyophilized powder to be reconstituted with water for injection.

5.1.2 Placebo

Not applicable.

5.2 Treatments Administered

5.2.1 Selection and Timing of Dose for Each Patient

The treatment regimen used in this study is selected based on a Phase 1b study assessing the pharmacokinetic (PK) and pharmacodynamic (PD) effects of 3 doses of LR769 (25, 75, 225 µg/kg) in hemophilia A or B patients, as well as from a Phase 3 study which confirmed the clinical efficacy of 75 and 225 µg/kg LR769 for the treatment of bleeding episodes predicted based upon the PK/PD correlation in the Phase 1b trial. Based upon the demonstrated PK/PD relationship as well as the efficacy noted for achieving hemostasis in mild/moderate bleeding episodes, the initial dosing will employ 75 µg/kg prior a minor surgical procedure. However, to account for the more extensive tissue damage in major surgical procedures and resulting greater hemostatic challenge, a dose of 200 µg/kg before a major surgical procedure will be used. These doses are expected to provide a PD effect that will be sufficient to effectively prevent excessive bleeding during and after surgical/invasive procedures and achieve and maintain hemostasis. Additional doses for the post-procedure setting are outlined in detail in Sections 5.2.2 and 5.2.3 below.

Preliminary efficacy and safety results of a study ([RB-FVIIa-006-13, PERSEPT 1](#)) in patients 12 years and older provide evidence that on-demand LR769 doses of 75 µg/kg every 2-3 hours effectively control bleeding episodes in hemophilia A or B patients with inhibitors. The available results of this study and of the Phase 1b study completed earlier are more extensively described in the current LR769 [Investigator's Brochure](#).

5.2.2 Treatment for Major Surgical Procedures

The initial dose of LR769 (200 µg/kg) will be followed by repeated administration of 75 µg/kg of LR769 every 2 hours (±5 minutes) for the first 48 hours after completion of the procedure. The minimum duration of LR769 treatment for major procedures will be 5 days, according to the frequency listed in the [table below](#).

Table 1. Dose(s) and Dosing Schedule(s) for Major Surgical Procedures

Day	Dose	Recommended Frequency
Day 0 (within 2 minutes of surgical incision or invasive procedure)	200 µg/kg	Initial dose
Day 0 (post first dose) – 48 hours	75 µg/kg	Every 2 hours (±5 minutes)
Days 3- 4	75 µg/kg	Intervals of up to every 4 hours but not more frequently than every 2 hours
Days 5-6	75 µg/kg	Intervals of up to every 6 hours but not more frequently than every 2 hours
Days 7-10	75 µg/kg	Intervals of up to every 8 hours but not more frequently than every 2 hours
Day 11 to Last Administration of LR769	75 µg/kg	Intervals of up to every 12 hours but not more frequently than every 2 hours

NOTE: If clinically indicated because of oozing or similar findings suggesting the need for more frequent LR769 infusions, the treatment interval may be shortened in consecutive doses within the guidelines stated in Table 1.

If the patient requires further treatment with LR769 after hospital discharge, the patient will administer LR769 at home according to the investigator’s judgment and the dosing guidelines specified in Table 1. The patient will be provided with LR769 and directions for its storage, reconstitution and administration along with a patient diary in which to record LR769 administration.

If physical therapy is planned, an IV bolus dose of 75 µg/kg of LR769 administered within ≤2 minutes is recommended each time before the therapy begins. Similarly, before drain or suture removal, an IV bolus dose of 75 µg/kg of LR769 administered within ≤2 minutes is recommended.

5.2.3 Treatment for Minor Surgical or Other Invasive Procedures

The initial dose of LR769 (75 µg/kg) will be followed by repeated administration of 75 µg/kg of LR769 every 2 hours (±5 minutes) for the first 48 hours. The minimum duration

of LR769 infusion for minor procedures will be 2 days, according to the frequency listed in the table below.

Table 2. Dose(s) and Dosing Schedule(s) for Minor Surgical or Other Invasive Procedures

Day	Dose	Recommended Frequency
Day 0 (within 2 minutes of surgical incision or invasive procedure)	75 µg/kg	Initial dose
Day 0 (post first dose) – 48 hours	75 µg/kg	Every 2 hours (±5 minutes) initially. Interval may be increased upon the investigator's judgment
Day 3 to Last Administration of LR769	75 µg/kg	Intervals of up to every 24 hours but not more frequently than every 2 hours

*For less invasive procedures, such as PICC or Port-a-Cath placement and for procedures such as dental extractions, the patient may be treated for ≤48 hours if the investigator or designee determines this shorter duration of treatment is sufficient to achieve hemostasis.

NOTE: If clinically indicated because of oozing or similar findings suggesting the need for more frequent LR769 infusions, the treatment interval may be shortened in consecutive doses within the guidelines stated in Table 2.

5.2.4 All Procedures

If the patient requires further treatment with LR769 after discharge, the patient will administer LR769 at home according to the investigator's judgment and the dosing guidelines in [Sections 5.2.2](#) and [5.2.3](#). The patient will be provided with LR769 and directions for its storage, reconstitution and administration along with a patient diary in which to record LR769 administration.

5.3 Method of Assigning Patients to Treatment Groups

The method of assigning patients to treatment groups is not applicable as this is a study with a single treatment group.

5.4 Blinding

Not applicable.

5.5 Concomitant Therapy

All concomitant therapies, including the use of blood products such as red blood cells, platelets, fresh frozen plasma, fibrinogen, etc, will be recorded in the patients' medical records and/or patients' diaries and in the eCRF. Concomitant therapies, including date, time, and dose, will be recorded from 30 days prior to screening and throughout the study until the end of the follow-up period.

5.6 Restrictions

5.6.1 Prohibited Medications

All aspirin, NSAIDs, herbs, natural medications, or any other drug with platelet inhibitory properties must be discontinued at least 1 week prior to elective surgical or other invasive procedure and for the duration of treatment with LR769.

Additional restrictions to concomitant therapies include the use of other sources of FVIIa, such as aPCC (FEIBA[®]) or NovoSeven[®]. These products may be used only if the response to LR769 is considered insufficient (ie, treatment failure), in which case these bypassing agents may be used for rescue therapy.

Other agents for the prevention of excessive bleeding during surgical or other invasive procedures, such as antifibrinolytics, are allowed and will be recorded on the eCRF.

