6.8 Efficacy Assessments

Efficacy Assessments:

The intraoperative efficacy of LR769 will be assessed by the surgeon/practitioner; all other efficacy assessments will be made by the investigator or designee as specified in [Appendix 1](#). Assessments for major and minor procedures will be performed at the same timepoints.

The final assessment (which represents the primary efficacy outcome) will be performed by the investigator at the study center 48 (± 4) hours after the last dose of LR769 and will be based upon the totality of the assessments performed on the patient at each timepoint, also taking into consideration the number of (interventions for) bleeding episodes, oozing, blood transfusions, and the total amount of LR769 used.

All efficacy assessments will be recorded in the patient's source records and on the eCRF.

Intraoperative Assessment of Efficacy by Surgeon/Practitioner

The surgeon/practitioner's rating of intraoperative efficacy of LR769 will be based on the following parameters:

- Estimated blood loss in the surgical patient as compared to the maximum expected volume of blood loss in a patient without a bleeding disorder:
 - Prior to surgery, the surgeon will note if the procedure is major or minor and the type of anesthesia that is planned, and estimate the maximum expected volume of blood loss based upon the type of surgery and the surgeon/practitioner's previous experience in a patient who does not have a bleeding disorder. After the procedure, the surgeon/practitioner will determine the actual characteristics of the procedure and estimate the volume of blood lost during the procedure using the following factors as a guide: volume of drainage fluid, volume of fluid on sponges and towels, fluid replacement given, transfusion requirements, etc. The maximum expected volume of blood loss and the estimated volume of blood loss during the procedure will be recorded.
 - The surgeon/practitioner will assess the intraoperative hemostasis by comparing the estimated intraoperative blood loss with the maximum expected blood loss estimated prior to the procedure as well as the amount of fluid replacement given, transfusion requirements, hemodynamic stability, etc

Comments from the surgeon/practitioner may be necessary if extenuating circumstances occurred (eg, an artery was briefly severed and required additional time for surgical control of the bleeding creating a larger than expected blood loss.

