Taking into account the above parameters, the intraoperative response to treatment will be rated as follows:

- Excellent: intraoperative blood loss similar to or less than expected for this type of procedure in a patient who does not have a bleeding disorder and who is undergoing the same surgical or other invasive procedure; no blood component transfusion is required
- Good: intraoperative blood loss that is greater than expected (but not more than 50% greater) for this type of procedure in a patient who does not have a bleeding disorder and who is undergoing the same surgical or other invasive procedure; no unexpected increased blood component transfusion requirement
- Moderate: intraoperative blood loss that is substantially greater than expected (more than 50% greater) for this type of procedure in a patient who does not have a bleeding disorder and who is undergoing the same surgical or other invasive procedure, not explained by a surgical/medical issue other than hemophilia; additional blood component (within 2-fold greater than expected) transfusion is necessary
- Poor: uncontrolled intraoperative blood loss, not explained by a surgical/medical issue other than hemophilia, that requires intervention (rescue therapy requirement [bypass agent or porcine FVIII], and/or increased blood component [>2 -fold greater than expected] transfusion, and/or leads to hypotension or unexpected transfer to Intensive Care Unit [ICU])

Investigator or Designee Assessment of Hemostasis on Postoperative Days

- Excellent: postoperative blood loss similar to or less than expected following this type of procedure in a patient who does not have a bleeding disorder and who is undergoing the same surgical or other invasive procedure; no blood component transfusion is required
- Good: postoperative blood loss greater than expected following this type of procedure in a patient who does not have a bleeding disorder and who is undergoing the same surgical or other invasive procedure, not explained by a surgical/medical issue other than hemophilia; no unexpected need for blood component transfusion

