- Moderate: postoperative blood loss that is substantially greater than expected following this type of procedure in a patient who does not have a bleeding disorder and who is undergoing the same surgical or other invasive procedure, not explained by a surgical/medical issue other than hemophilia; additional blood component [within 2-fold greater than expected] transfusion is necessary
- Poor: uncontrolled postoperative blood loss, not explained by a surgical/medical issue other than hemophilia that requires intervention (rescue therapy requirement [bypass agent or porcine FVIII], and/or increased blood component [>2 -fold greater than expected] transfusion, and/or leads to hypotension or unexpected transfer to Intensive Care Unit [ICU])

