6.13 Removal of Patients from the Trial or Treatment

The investigator may withdraw a patient from the study for any of the following reasons:

- The investigator believes it is in the best interest of the patient to discontinue the study
- The Sponsor or investigator terminates the study
- The patient withdraws consent or requests to be discontinued from the study
- The patient is non-compliant

In case of early withdrawal of the patient, he will be asked to perform the 48 (\pm 4) hour visit assessment after last administration of LR769, unless he has withdrawn Informed Consent.

The investigator may discontinue a patient from LR769 treatment for any of the following reasons:

- AE or SAE possibly related to LR769 treatment
- A clinically significant change in the patient's condition that does not allow safe administration of LR769
- Per judgment of the investigator, if an adequate hemostatic response is not achieved with LR769, and the bleeding requires continued treatment, the treating physician should stop treatment with LR769 and treat the patient with a rescue therapy, such as another bypassing agent (e.g., FEIBA® or NovoSeven®) and/or other effective hemostatic treatment. The patient remains eligible for treatment with LR769 for a new surgical procedure taking into account the pharmacodynamic half-life of the rescue therapy given.

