9.5.1 Primary Efficacy Endpoint

The primary efficacy endpoint is the percentage of surgical or other invasive procedures with a “good” or “excellent” response to LR769 treatment as assessed by the investigator at the study center 48 (± 4) hours after the last administration of LR769; this assessment will be based upon the totality of assessments performed on the patient at each timepoint also taking into consideration the surgeon’s intraoperative hemostatic assessment, the number of (interventions for) bleeding episodes, oozing, blood transfusions, and the amount of LR769 used.

A point estimate of this endpoint will be calculated together with a Clopper-Pearson exact 95% confidence interval.

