7.7.1 Analysis of Primary Efficacy Endpoint

The primary efficacy endpoint is the percentage of surgical or other invasive procedures with a “good” or “excellent” response to LR769 treatment, as assessed by the investigator at the study center 48 (\pm 4) hours after the last administration of LR769; this assessment will be based upon the totality of assessments performed on the patient at each timepoint, also taking into consideration the surgeon’s intraoperative hemostatic assessment, the number of (interventions for) bleeding episodes, oozing, blood transfusions, and the amount of LR769 used. An additional sensitivity analysis will be performed in which patients whose 48-hour assessment is missing are treated as failures.

The proportion of “good” and “excellent” responses at 48 (\pm 4) hours will be summarized. Clopper-Pearson exact 95% confidence interval for proportion will be calculated for each surgery type and age group and overall. The summaries will include missing assessments in percent calculation, while they will still be discarded when calculating the proportion of successes and the confidence interval (CI). The missing values imputed as per section 7.3 of this SAP will be analyzed as imputed.

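### A procedure rescued with another bypassing agent can still count as an LR769 success, because the rating scale fails only some rescues and no analysis rule overrides a recorded 48-hour rating

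*Protocol*

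**What the plan says.** - **Label.** Protocol 5.6.1, on other sources of FVIIa: "These products may be used only if the response to LR769 is considered insufficient (ie, treatment failure").
- **What happens on an inadequate response.** Under Protocol 6.13, if the response is inadequate and the bleeding needs continued treatment, "the treating physician should stop treatment with LR769 and treat the patient with a rescue therapy". This stands among the reasons for discontinuing LR769, separately from the reasons for leaving the study. Patients who do withdraw early are still asked to attend the 48-hour visit unless they have withdrawn consent.
- **Rating scale.** In Protocol 6.8, postoperative *Poor* is "uncontrolled postoperative blood loss, not explained by a surgical/medical issue other than hemophilia that requires intervention (rescue therapy requirement [bypass agent or porcine FVIII"]), or excess transfusion, hypotension or unplanned intensive care. The surgeon's scale has a matching entry: "uncontrolled intraoperative blood loss, not explained by a surgical/medical issue other than hemophilia, that requires intervention (rescue therapy requirement [bypass agent or porcine FVIII"]).
- **Endpoint.** Protocol 9.5.1: "The primary efficacy endpoint is the percentage of surgical or other invasive procedures with a “good” or “excellent” response to LR769 treatment", rated by the investigator 48 (±4) hours after the last LR769 dose. It is a global judgement over all assessments. SAP 7.7.1 has the investigator decide while "also taking into consideration the surgeon’s intraoperative hemostatic assessment". The list in Protocol 6.8 omits that item and reads "also taking into consideration the number of (interventions for) bleeding episodes, oozing, blood transfusions, and the total amount of LR769 used".
- **Analysis rules that mention rescue or failure.** SAP 7.3 imputes *Poor* only when the final rating is missing, the patient left the study within 2 days of the last dose because of an adverse event or the investigator's decision, and an antihemorrhagic was used within 52 hours. SAP 7.7.1 adds a sensitivity analysis that counts missing 48-hour ratings as failures.

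**The concern.** The protocol calls the situation that permits rescue a treatment failure, but that label is not carried through to the primary analysis. The trial is single-arm and unblinded, and its primary endpoint is one investigator's global rating. LR769 is stopped when rescue begins, so the 48-hour rating can be made after another product has acted. If that rating is *Good* or *Excellent*, the procedure counts as an LR769 success in every planned analysis. With as few as 12 procedures, one such case visibly changes the estimate and its interval.

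**Working it through.** The documents state no power, null rate or success threshold, so there is no planned figure to reproduce. The check has two parts.

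**1. Does the scale fail every rescued procedure?**

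- To start rescue: an insufficient response (5.6.1), or an inadequate response with bleeding that needs continued treatment (6.13).
- To be rated *Poor*: blood loss that is uncontrolled, has no other surgical or medical explanation, and requires intervention. Bypassing agents and porcine FVIII are named as such interventions.
- To be rated postoperative *Good*: more loss than expected, and no unexpected transfusion. There is no upper limit on the loss (the intraoperative *Good* has one, at 50% above expected) and no exclusion of rescue.

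Rescue for uncontrolled hemophilic bleeding should be rated *Poor*. Rescue for bleeding that is inadequately controlled but not uncontrolled, without extra transfusion, meets 6.13 and can be read as *Good*. So can rescue where the investigator attributes the uncontrolled bleeding partly to a surgical cause: *Poor* then does not apply as written, and no text says which category does.

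**2. Does the analysis catch what the scale misses?**

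- SAP 7.3 needs a missing rating. Stopping LR769 for inadequate response is not study withdrawal, and the 48-hour visit is requested even after early withdrawal, so a rescued procedure can well have a rating.
- The SAP 7.7.1 sensitivity analysis also needs a missing rating.
- No rule compares a recorded rating with recorded rescue.

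**3. Size, for scale only.** Inputs: at least 12 procedures, of which at least 6 are major (Protocol 3.3, SAP 4); Clopper-Pearson 95% interval (Protocol 9.5.1). For x successes in n, the lower limit is the 0.025 quantile of Beta(x, n−x+1) and the upper limit the 0.975 quantile of Beta(x+1, n−x). For x = n the lower limit is 0.025^(1/n); for 12/12, 0.025^(1/12) = 0.735.

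| Successes | Estimate | 95% interval |
|---|---|---|
| 12/12 | 100% | 73.5 to 100 |
| 11/12 | 91.7% | 61.5 to 99.8 |
| 10/12 | 83.3% | 51.6 to 97.9 |
| 6/6 major | 100% | 54.1 to 100 |
| 5/6 major | 83.3% | 35.9 to 99.6 |

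One reclassified procedure costs 100 − 91.7 = 8.3 points on the estimate and 73.5 − 61.5 = 12.0 points on the lower limit. Among six major procedures the costs are 100 − 83.3 = 16.7 and 54.1 − 35.9 = 18.2 points.

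The chance of at least one rescue in 12 is 1 − (1 − p)^12. At assumed rates p of 5%, 10% and 20% it is 46%, 72% and 93%. This treats procedures as independent, although one patient may contribute several. It is the chance of a rescue, not of a misclassified one.

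**The case against.** A reader might infer that nothing in the plan links rescue to failure once a rating exists. The documents do not support that. *Poor* names bypassing-agent and porcine FVIII rescue on both scales, and *Poor* is a primary-endpoint failure. *Good* after rescue for uncontrolled hemophilic bleeding would contradict the scale.

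A reader might also infer that a rescue during surgery drops out because the postoperative scale rates only postoperative loss. But Protocol 9.5.1 and SAP 7.7.1 require the surgeon's rating to be considered, and even the shorter list in 6.8 refers to all assessments at each timepoint. Interventions for bleeding are on every version of the list, which covers rescue in substance. A rating is also due at the last LR769 dose (Protocol 7.4).

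Two further inferences lack a source: that the whole 48 hours would be spent on rescue treatment (no duration is given), and that a small amount of LR769 used would be read as favorable.

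Finally, efficacy is descriptive, no threshold is at stake, and the planned listings of ratings, bleeding episodes and concomitant medications would let a careful reader find a discordant case.

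All of this stands, and it narrows the point without removing it. Considering an earlier *Poor* is not the same as carrying it forward. The gap between inadequate and uncontrolled bleeding is in the text. Listings expose a discordant case only afterwards and do not change the reported percentage.

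**Conclusion.** The point holds in a limited form. The scale fails some rescued procedures and leaves the rest to unblinded judgement. The analysis has no rule for a rescued procedure with a recorded rating, although 5.6.1 describes the ground for rescue as treatment failure. At the 12-procedure minimum, with all other procedures successful, each case is worth 8.3 points on the estimate and 12.0 points on the exact lower limit.

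A reader might go on to infer that the primary result will be biased upward. That cannot be said: the documents give no rescue rate, and the harm needs both a rescue and a rating of *Good* or *Excellent* after it. This is a gap in the endpoint definition that should be closed before database lock. It does not invalidate the plan.

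**What to change.** Add to SAP 7.7.1 and Protocol 9.5.1:

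> Any procedure in which another bypassing agent (another FVIIa source, including aPCC) or porcine FVIII was given between the first LR769 dose and the 48 (±4) h assessment is counted as a failure for the primary endpoint, whatever rating was recorded.

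Report the as-rated result as a sensitivity analysis. In Protocol 6.8, add the intraoperative rating to the list of considerations so that it agrees with 9.5.1.

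Keep the rule to these named products. The whole antihemorrhagics ATC subgroup used in SAP 7.3 may take in antifibrinolytics (an assumption, since the documents do not list its content), which 5.6.1 permits. A wider category of other hemostatic rescue would need the reason for use, which is not among the concomitant-treatment items in Protocol 5.5 and 6.11. The price is that rescue with other hemostatic treatment, which 6.13 also allows, stays with the investigator's rating.

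**Cost.** No new data: product, date, time and dose are already recorded. SAP 7.1 calls for a protocol amendment when a change may affect the primary conclusions. The reported success rate may be slightly lower. The rule changes how outcomes are counted, not how patients are treated.
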